4.5.3 Deaths

4.5.3.1 Presentation

A summary of deaths will be provided with the number and percentage of participants categorized as:

- Related to disease under investigation only
- AE outcome = death only
- Both related to disease under investigation and with AE outcome = death
- AE with outcome = death > 30 days after last study intervention
- Other deaths

A corresponding listing will also be produced.

4.5.4 Clinical Laboratory, Blood Sample

4.5.4.1 Definitions and Derivations

Laboratory tests are grouped according to chemistry, hematology and coagulation. Laboratory parameters will be assessed at baseline as well as throughout the study.

For chemistry and hematology parameters, laboratory abnormalities with toxicity grades according to the NCI CTCAE version 5.0 will be derived.

Laboratory variables that will be measured are detailed in Table 17 of the CSP.

Change from baseline in hematology, clinical chemistry and coagulation endpoints will be calculated for each post-dose visit. CTC grade is calculated at each visit for tests with CTC grading defined. Maximum on-intervention CTC will be also calculated. Absolute values will be compared to the local laboratory reference range and classified as low (below range),

normal (within range or on limits of range) and high (above range). All values classified as high or low will be flagged on the listings.

Liver Function Parameters

Number and percentage of participants with elevated post-baseline ALT, AST, or Total Bilirubin will be tabulated. Individual participant data where elevated ALT or AST plus total bilirubin fall into the "Potential Hy's law" will be summarized and listed.

4.5.4.2 Presentations

The change in each laboratory parameter from baseline to each post-baseline visit may be summarized graphically.

Laboratory abnormalities occurring from the start of IP administration to the last assessment on treatment will be presented. Worst toxicity grade, rates of grade 3 or higher toxicity, and grade shifts of 2 or more from baseline to the maximum grade may be presented. Summaries indicating hyper- and hypo- directionality of change are produced, where appropriate. Laboratory parameters that cannot be graded via NCI CTCAE are summarized with frequencies of post-baseline laboratory values categorized as low (L), normal (N), or high (H) using laboratory normal ranges compared to baseline.

Listings are provided for all laboratory results.

4.5.5 Clinical Laboratory, Urinalysis

4.5.5.1 Definitions and Derivations

Urinalysis variables that will be measured are detailed in Table 17 of CSP.

CTC grade will be calculated for urinalysis at each visit. Maximum on treatment CTC will be also calculated. Absolute values will be compared to the local laboratory reference range and classified as low (below range), normal (within range or on limits of range) and high (above range). All values classified as high or low are flagged in the listings.

4.5.5.2 Presentations

Shift tables ("Negative", "Trace", "Positive", "0", "+", "++", "+++") from baseline to worst on-intervention results may be produced for urinalysis.

Listings will be provided for all laboratory results including urinalysis.

4.5.6 Vital Signs

4.5.6.1 Definitions and Derivations

Body temperature, blood pressure, pulse rate, and respiratory rate and pulse oximetry will be assessed at baseline and throughout the study.

Normal ranges for vital signs are presented in Table 5.

Table 5 Vital Sign Normal Ranges

VS Test	Outside AZ defined reference range lower limit if	Outside AZ defined reference range upper limit if
BMI	< 18	>25
Temperature (C)	< 36	> 37.5
Systolic Blood Pressure (mmHG)	< 90	> 140
Diastolic Blood Pressure(mmHG)	< 60	> 90
Pulse rate	< 60	> 100
Respiratory rate (min)	< 12	> 20
Pulse rate	< 60	> 100
Oxygen saturation (%)	< 94	NA

4.5.6.2 Presentations

Vital signs will be summarized by study visit which may include descriptive statistics for the value of the parameters and the changes from baseline.

Absolute values and change from baseline for vital signs data at each timepoint may be presented using box plots.

4.5.7 Electrocardiogram

4.5.7.1 Definitions and Derivations

Electrocardiogram (ECG) parameters will be assessed at baseline as well as throughout the study. ECG parameters include: PR, RR, QRS, QT and QTcF. The QTcF is considered as the primary correction method to assess participant cardiac safety.

The ECGs will be performed in triplicate (all 3 ECGs to be performed within a 5-minute time period, at least 1 minute apart). For triplicate ECGs, the mean of the three ECG assessments will be used to determine the value at that time point. Baseline of ECG is the mean of last three ECG assessments prior to first dose. If only two ECG assessments prior to first dose are available, then take the average of these last two ECG assessment prior to first dose as baseline of ECG; if only one ECG assessments prior to first the dose is available, then take the last one ECG assessment prior to the first dose as baseline of ECG.

From these resting 12-lead ECGs values of the QT and RR intervals and the QT interval corrected for heart rate using Fridericia's correction (QTcF) is derived using the following formula:

QTcF = QT/RR^ (1/3) where RR is in seconds

The values of QTcF (milliseconds) are re-derived from the values of RR and QT during the creation of the reporting database.]

The notable ECG interval values while on treatment are:

- Maximum QTcF intervals > 450 milliseconds, > 480 milliseconds, and > 500 milliseconds
- Maximum changes from baseline in QTcF > 30, >60, and > 90 milliseconds.

Normal ranges for ECG are presented in Table 6.

Table 6 ECG Normal Ranges

ECG Parameter	Outside AZ defined reference range lower limit if	Outside AZ defined reference range upper limit if
Heart rate (bpm)	< 40	> 100
RR (msec)	< 600	> 1200
PR (msec)	< 120	> 200
QRS (msec)	< 60	> 109
QT (msec) and QTcF (msec)	< 320	> 450

4.5.7.2 Presentations

ECG parameters will be summarized using descriptive statistics by visit and change from baseline in ECG endpoints are calculated for each post-dose visit. Absolute values and change from baseline for ECG data at each timepoint may be presented using box plots.

The number and percentage of participants having notable ECG interval values while on treatment are summarized.

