- e Participants with active hepatitis A, B, or C are excluded. Participants who have chronic hepatitis B and receiving suppressive antiviral therapy are allowed on study if ALT is normal and viral load is controlled; controlled hepatitis B viral load is defined as serum hepatitis B virus DNA < 100 IU/mL by PCR. Participants who have chronic hepatitis C are allowed to be enrolled if ALT is normal and hepatitis C virus RNA is undetectable by PCR, either spontaneously or in response to a successful prior course of antihepatitis C therapy.

- f A urine or serum pregnancy test is acceptable; if urine test is positive or equivocal, then serum  $\beta$ -hCG testing should be performed for confirmation.
- g For participants in mainland China only, samples will not be collected.
- h Recent biopsy within the last 4 months is required for participants in Part A mini-expansion and Part B unless medically contraindicated. Within that time period, participant must not have received any anti-cHL treatment since the last line of therapy, otherwise fresh tissue is required. For participants in Part A Dose Escalation, tumor tissues biopsy within prior 4 months is optional.
- i AstraZeneca may request prior images/scans performed up to 6 months prior to start of study intervention.

Clinical Study Protocol - Version 5 Sabestomig (AZD7789) - D9571C00001

Abbreviations: AE: adverse event; ALT: alanine transaminase; COVID-19: coronavirus disease 2019; ECG: electrocardiogram; FEV1: forced expiratory volume over 1 second; FVC: forced vital capacity; HIV: Human immunodeficiency virus; PCR: polymerase chain reaction; SAE: serious adverse event.

Study Period	Intervention Period							
Visit	V2	V3	V4	V5	V6	V7	V8-Vn	
Cycle Number and Day	C1D1	C1D3	C1D8	C1D15	C2D1	C2D8	C3D1-CnD1 a	
Procedure/Window			± 1 D	± 3 D	±1 D	± 3 D	± 3 D	
Abbreviated (symptom-directed) physical examination including weight (Section 8.2.2) b	Х		X	Х	X b	Х	X b	
12-lead ECG (triplicate) (Section 8.2.4) c	X °		X		X °	Х	C3D1 °, C4D1 °, and as clinically indicated thereafter	
Left ventricular ejection fraction by echocardiogram/ multiple-gated acquisition scan (Section 8.2.5) d	As clinically indicated							
Vital signs including pulse oximetry (Section 8.2.3) e	X °		Х	X	X e	Х	X °	
Eastern Cooperative Oncology Group performance status (Section 8.2.6)	х				Х		Х	

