#### Table 3Schedule of Activities for the Intervention Period (Part B Dose Expansion)

Table 3	Schedule of Activities for the Intervention Period (	(Part B Dose Expansion)

Study Period	Intervention Period					
Visit	V2	V3	V4	V5	V6	V7-Vn
Cycle Number and Day	C1D1	C1D8	C1D15	C2D1	C2D8	C3D1-CnD1
Procedure/Window		± 1 D	± 3 D	± 1 D	± 3 D	± 3 D
Disease Assessments						
Imaging disease assessment (Section 8.1, Table 16) t	At least 10 days after sabestomig administration in Cycle and then thereafter at Year 1 from the date of the first infusion, then Q6M until PD, start of new treatment for HL or EoS (whichever occurs first). Of Note: if a participant in CR receives RT as consolidation, imaging disease assessment should continue until the participant meet the criteria mentioned in the paragraph above.					

a On dosing days, the physical examination will be conducted prior to sabestomig administration.

b All ECGs will be obtained in triplicate (all within a 5-minute time period). Collection times for ECGs on days of sabestomig administration are shown below. Whenever ECGs and blood draws (eg, PK/ADA) are scheduled for the same nominal time, the blood draws should occur last. The timing of the ECG should be such that it allows the blood draw to occur at the proper nominal time. Day 8 assessment only to be performed if cardiac signal is detected in Part A.

Collection Times for ECGs on Sabestomig Dosing Days						
Cycle Number and DayPrior to SOI (within 30 mins prior to SOI)1 h (± 5 mins) Post EOI						
C1D1, C2D1, C3D1, and C4D1	Х	Х				
C5D1, C6D1, etc.	As clinically indicated					

c If clinically indicated, and at the Investigator's discretion, a consultation with a cardiologist is recommended for follow-up.

d Collection times for vital signs and pulse oximetry on days of sabestomig administration are shown below. Whenever vital signs and blood draws (eg, PK/ADA) are scheduled for the same nominal time, the blood draws should occur last. The timing of the vital signs assessment should be such that it allows the blood draw to occur at the proper nominal time.

Collection Times for Vital Signs and Pulse Oximetry on Sabestomig Dosing Days						
Cycle Number and Day	Prior to SOI (within 30 mins prior to SOI)	EOI (± 5 min)	30 mins (± 10 min) Post EOI			
C1D1	Х	Х	Х			
C2D1, C3D1, C4D1, etc.	Х		Х			

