Abbreviations: ADA: anti-drug antibody; AE: adverse event; anti-HBc: hepatitis B core antibody; anti-HBs: antibody to hepatitis B surface antigen; C: cycle; COVID-19: coronavirus disease; CR: complete response; CT: computed tomography; D: day(s); ECG: electrocardiogram; EOI: end of infusion; COVID-19: coronavirus disease; CR: complete response; CT: computed tomography; D: day(s); ECG: electrocardiogram; EOI: end of infusion; COVID-19: coronavirus disease; CR: complete response; CT: computed tomography; D: day(s); ECG: electrocardiogram; EOI: end of infusion; COVID-19: coronavirus disease; CR: complete response; CT: computed tomography; D: day(s); ECG: electrocardiogram; EOI: end of infusion; COVID-19: coronavirus disease; CR: complete response; CT: computed tomography; D: day(s); ECG: electrocardiogram; EOI: end of infusion; COVID-19: coronavirus disease; CR: complete response; CT: computed tomography; D: day(s); ECG: electrocardiogram; EOI: end of infusion; COVID-19: coronavirus disease; CR: complete response; CT: computed tomography; D: day(s); ECG: electrocardiogram; EOI: end of infusion; COVID-19: coronavirus disease; CR: complete response; CT: computed tomography; D: day(s); ECG: electrocardiogram; EOI: end of infusion; COVID-19: coronavirus disease; CR: complete response; CT: complet

; EoS: end of study; EoT: end of treatment; CC

; HbsAg: hepatitis B surface antigen; h: hour; HL: Hodgkin lymphoma; min: minute; PCR: polymerase chain reaction; PD: progressive disease;
 ; PET-CT: positron emission tomography-CT; PF: pediatric short form; PGI-TT: Patient Global Impression of Treatment Tolerability;
 PGIC: Patient Global Impression of Change;
 CCI
 <li

PRO-CTCAE: Patient-Reported Outcomes version of the Common Terminology Criteria for Adverse Events; Q1W: every week; Q3W: every 3 weeks; Q6M: every 6 months; Q6W: every 6 weeks; RECIL: Response Evaluation Criteria in Lymphoma; RT: radiation therapy; SAE: serious adverse event; SF: short form; SOI: start of infusion; TIM-3: T cell immunoglobulin and mucin domain-containing protein-3; V: visit.

	At Disease Progression a	EoT b	Post-treatment Safety Follow-up c		Survival Follow-up c	
Procedure/Visit (Window)		+ 14 D	Day 30 Post Last Dose (± 7 D)	Day 90 Post Last Dose (± 7 D)	Q6M Post Last Disease Assessment (± 14 D)	
Abbreviated (symptom-directed) physical examination including weight (Section 8.2.2)		Х	Х	Х		
12-lead ECG (triplicate) (Section 8.2.4)		X				

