3.3.2 Visit Window

For safety and tumor assessments, visit windows are defined for any presentations that summarise values by visit. The following conventions apply:

For tumor assessments:

 The protocol assigned windows for tumor assessments will be used to assign the result to a particular visit.

For safety assessments:

- Visit windows will be exhaustive so that data recorded at any timepoint has the potential
 to be summarized. Inclusion within the visit window will be based on the actual date and
 not the intended date of the visit.
- All unscheduled visit data have the potential to be included in the summaries.
- The window for the visits following baseline will be constructed in such a way that the
 upper limit of the interval falls half way between the two visits (the lower limit of the
 first post-baseline visit is Day 2). If an even number of days exists between two
 consecutive visits then the upper limit is taken as the midpoint value minus 1 day.
- If treatment cycle delays are experienced, the planned dosing visit windows will be
 modified during the programming to anchor to the actual visit date where intervention
 was administered on to adjust for these treatment cycle delays. The same rules apply to
 safety visits of other types (non-dosing visits) where the safety visit is moved due to a
 treatment cycle delay.
- Visit windowing will be done separately for each assessment based on the schedule of events specific to that assessment. See Appendix B for details.
- For summaries showing the maximum or minimum values, the maximum/minimum value recorded on treatment will be used (regardless of where it falls in an interval).

- Listings should display all values contributing to a time point for a participant.
- For visit based summaries, if there are more than one value per participant within a visit window then the closest value to the scheduled visit date will be summarized, or the earlier, in the event the values are equidistant from the nominal visit date. If there is still a tie, preference to the nominal visit at which the results were reported at will be given. The listings will highlight the value for the participant that contributed to the summary table, wherever feasible. Note: in summaries of extreme values, all post baseline values collected will be used including those collected at unscheduled visits regardless of whether or not the value is closest to the scheduled visit date.

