4.5.8 Echocardiogram/Multiple-gated Acquisition Scan (ECHO/MUGA)

4.5.8.1 Definitions and Derivations

Left ventricular ejection fraction (LVEF) will be measured by ECHO or MUGA scan at screening, end of treatment (EOT), and as clinically indicated during the study.

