4.5.8.2 Presentations

Absolute value, change from baseline and percentage change from baseline will be presented for LVEF.

Box plots of absolute value and change from baseline over time may also be presented

The overall evaluation (normal/abnormal) will be summarized over time.

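### SAP Appendix B gives ECG a Cycle 5 Day 1 window although routine ECGs end at Cycle 4 Day 1, so by-visit ECG summaries after that point would describe a clinically selected subset

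*SAP*

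**What the plan says.** **Collection.** Protocol Section 1.3, Table 2 (Part A) places ECGs at C1D1, C1D8, C2D1, C2D8, C3D1 and C4D1, "and as clinically indicated thereafter". Table 3 (Part B) has the same rule. Its timing footnote fixes the dosing-day ECGs at "C1D1, C2D1, C3D1, and C4D1", leaves C5D1 onward to clinical indication, and makes the Day 8 ECG conditional on a cardiac signal in Part A. Table 4 adds one ECG at EoT and none at the other follow-up visits.

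**Status.** Protocol Section 3, Table 5 includes change from baseline in ECG results in the primary safety endpoints of both parts.

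**Analysis.** SAP Section 4.5.7.2 states: "ECG parameters will be summarized using descriptive statistics by visit and change from baseline in ECG endpoints are calculated for each post-dose visit". It also allows box plots at each timepoint. SAP Section 3.3.2 says "Visit windows will be exhaustive so that data recorded at any timepoint has the potential" to be summarised, and "All unscheduled visit data have the potential to be included in the summaries". The same section says that windowing follows the schedule specific to each assessment. SAP Section 3.3.1 counts data as on treatment up to 90 days after the last dose, if before further cancer therapy. The ECG columns of Appendix B include C5D1, Days 75–95, for Part A and for Part B. No EoT window is shown.

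**LVEF (secondary).** SAP Section 4.5.8.1 has LVEF measured at screening, "end of treatment (EOT), and as clinically indicated during the study". Section 4.5.8.2 adds: "Box plots of absolute value and change from baseline over time may also be presented".

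**The concern.** Up to C4D1 the by-visit ECG series describes essentially everyone still on treatment. After C4D1, a participant appears only if a clinician had a reason to record an ECG, or possibly because treatment ended. The table and box plot look continuous across that boundary, but the group behind them changes.

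A step between C4D1 and C5D1 could then come from who was measured rather than from the drug. Myocarditis is a named potential risk (Protocol Section 2.3.1), so an apparent late shift could be read as delayed cardiac toxicity. Conversely, a few unremarkable late values could be taken as reassurance about a period with no routine ECGs.

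**Working it through.** **1. Reproduce the SAP's ECG windows.** Inputs: the three-week cycle puts Day 1 of cycle k on study day 1 + 21 × (k − 1). The nominal ECG days are therefore C1D1 = 1, C1D8 = 8, C2D1 = 22, C2D8 = 29, C3D1 = 43, C4D1 = 64; the next two dosing days are C5D1 = 85 and C6D1 = 106. Under SAP Section 3.3.2 the first post-baseline window opens on Day 2. Each upper limit is halfway to the next visit, reduced when an even number of days lies between the two visits (a half-day midpoint is rounded up, then 1 day is subtracted).

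| Visit | Next visit | Midpoint | Upper limit | Window | Appendix B |
|---|---|---|---|---|---|
| C1D8 (8) | 22 | 15 | 15 | 2–15 | 2–15 |
| C2D1 (22) | 29 | 25.5 | 25 | 16–25 | 16–25 |
| C2D8 (29) | 43 | 36 | 36 | 26–36 | 26–36 |
| C3D1 (43) | 64 | 53.5 | 53 | 37–53 | 37–53 |
| C4D1 (64) | 85 | 74.5 | 74 | 54–74 | 54–74 |
| C5D1 (85) | 106 | 95.5 | 95 | 75–95 | 75–95 |

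All six agree. The last row arises only if C5D1 and C6D1 are treated as ECG visits, and the protocol schedules an ECG at neither. On the protocol's own ECG schedule, the last routine on-treatment window is C4D1, opening on Day 54, and there is no C5D1 window.

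**2. Extent of the uncovered period.** Treatment lasts at most 35 cycles (Protocol Sections 4.1.1 and 4.1.2). Cycles without a routine dosing-day ECG: 35 − 5 + 1 = 31 (Cycles 5 to 35).

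**3. Which ECGs can fall in Days 75–95.** Clinically indicated ECGs can, because unscheduled data are admissible. An EoT ECG in those days also could: it counts as on treatment and has no window of its own in the table as shown. A delayed C4D1 ECG should not, because the SAP re-anchors windows to actual dosing visits after a cycle delay.

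**4. Illustration of size (every input assumed; none is in the documents).** Let p be the share of on-treatment participants with an indicated ECG, m their mean QTcF change, and e the share with an EoT ECG in the window, with mean change 0. Everyone else has mean change 0.

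- Displayed mean = p × m / (p + e); mean over all participants = p × m; share contributing = p + e.
- Ranges tried: p = 2–10%, e = 5–10%, m = 10–30 ms.
- Lowest displayed mean: 0.02 × 10 / 0.12 = 1.7 ms (all participants: 0.2 ms).
- Highest: 0.10 × 30 / 0.15 = 20 ms (all participants: 3 ms).
- Share contributing: 7% to 20%.
- If no EoT ECG enters the window, the displayed mean is simply m, 10–30 ms by assumption.

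**5. Where a mean would be printed.** SAP Section 3.3.1 shows only n, minimum and maximum below 3 participants, and only lists dose levels with a single participant. Part A cohorts hold 1 participant, or 3 to 12 (SAP Section 3.3.7.2). At the top of the assumed range, 20% × 12 = 2.4, still below 3. Three contributors need 3 / 0.20 = 15 participants on treatment at 20% coverage, or 3 / 0.07 = 43 (rounded up) at 7%. The Part B cohort sizes are redacted. SAP Section 3.3.7 gives about 180 in total and up to 52 in Part A, leaving about 180 − 52 = 128 for the two Part B cohorts. Fewer will still be on treatment at Cycle 5.

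**The case against.** The other side has real points.

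- **The SAP already has the right rule.** Windowing by each assessment's schedule would produce no C5D1 ECG window, so the fault is closer to a table row that contradicts its own text than to a mistaken method. Much of the surrounding wording is permissive: unscheduled data may enter and box plots are optional. This stands, and it lowers the severity. But a programmer working from Appendix B would build the window, and nothing in Section 4.5.7.2 limits the output to scheduled visits.
- **There are safeguards.** The displayed n would reveal the drop in numbers, and the under-3 rule removes most Part A means. Neither tells the reader why the remaining participants were measured, and neither protects a larger Part B cohort.
- **Little is decided on these summaries.** No formal hypothesis is tested (Protocol Section 9.1), the Part B safety triggers are based on adverse events and treatment discontinuations due to them (Section 4.5), and the notable-QTcF categories use on-treatment maxima. All true; the problem is confined to the by-visit tables and plots.
- **LVEF is weakly attached.** It is not named in the primary safety endpoint, has no window in Appendix B, and its sampling basis is stated just before its presentation. It belongs here only as a secondary point.

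A reader might infer more than the documents support. Late ECGs cannot be said to come only from participants with symptoms or a cardiac problem: clinical indication is broader, and a laboratory value or a concomitant drug could also prompt one. Separate windows for every later cycle are not shown; the safety window tables stop at C5D1 for every assessment and may be incomplete. For the same reason, the entry of EoT ECGs into the C5D1 window is possible but not established.

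**Conclusion.** The point holds as an inconsistency between the ECG schedule and the SAP. Followed as written, the C5D1 ECG summary of a primary safety endpoint would describe a clinically selected subset, possibly mixed with EoT values. That the selection exists follows from the schedule alone; its effect on the mean does not.

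The size is unknown. The 1.7–20 ms range rests entirely on assumed rates and means and should not be read as a forecast, and the documents do not support any claim that a false late-QTcF signal is likely. The concern lies mainly in the Part B cohorts. The maximum-QTcF and maximum-change results are unaffected. Severity is minor.

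**What to change.** - **Appendix B:** remove the C5D1 ECG window in both parts. Keep the upper limit of C4D1 at Day 74; otherwise the exhaustive-window rule would leave C4D1 open-ended from Day 54 and move later ECGs into it. Give EoT its own timepoint.
- **Section 4.5.7.2:** restrict by-visit ECG summaries and box plots to protocol-scheduled ECG visits, including C1D8 and C2D8 in Part A, and the Day 8 ECGs in Part B only where the Part A cardiac-signal condition makes them required.
- **Clinically indicated ECGs:** list them, and keep them in the on-treatment maximum QTcF and maximum-change categories.
- **Section 4.5.8.2 (secondary):** present LVEF at baseline and EoT with the change between them, and list clinically indicated values.

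The cost is SAP wording and programming. No assessment is added or removed, and no data are lost.
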